### 9.1.2 Self-controlled Risk Interval Design

A complementary approach for Primary Objectives 3 and 4, an SCRI analysis, will be used to assess relative risks for AESIs meeting the criteria for this specific design (ie, acute onset, short latency, risk intervals that are relatively well known, that the occurrence of the event must not affect the probability of vaccination, and that the occurrence of the event of interest must not censor or affect the observation period) (Weldeselassie et al 2011). The SCRI is a case-only study that includes only individuals who were vaccinated with AZD1222 who experienced an outcome during the study period (Tokars et al 2012). The IRR comparing the IR of the AESI(s) in a period hypothesised to be at increased risk due to exposure (“risk period” or “exposed person-time”) will be compared with a prespecified postvaccination period within the same individual that falls after the risk period (“control period” or “unexposed person-time”). Limiting the selection of control periods to after vaccination will minimise the potential biases of other self-controlled designs that include comparator time before vaccination and require the assumption that prevaccination events do not affect the probability of subsequent vaccination (Weldeselassie et al 2011). Figure 1 illustrates the design of the SCRI analysis.

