### 9.2.3.2 SCRI Design: Follow-up and Time at Risk

The SCRI will be used for most of the AESI with known risk windows as per [Table 3](#). The SCRI evaluates occurrence of a particular AESI during a “risk interval” (exposed -person time) and a subsequent “control interval” (unexposed person-time) following vaccination with AZD1222 ([Figure 1](#)). Proposed outcome-specific risk intervals for the AESIs appear in [Section 9.3.2](#). Control intervals, which by design occur following the risk intervals, will have the same duration as the risk interval, except under the special circumstances explained below.

[Figure 1](#) illustrates this arrangement for a risk window that starts 1 day after vaccination and continues for 42 days. After a 7-day washout period, the control interval begins and ends after 42 days as well. It is important to note that in contrast to the cohort design, the occurrence of the outcome is not a censoring event for SCRI evaluation; the full duration of the risk interval and control intervals factors into the analysis. For subjects who receive a second dose, corresponding risk and control intervals follow the second dose as well.

In general, if the AESI occurs after dose 1 but before dose 2, the SCRI analysis includes only the risk and control intervals following dose 1. Similarly, if the AESI occurs after dose 2, the SCRI analysis includes only the risk and control intervals following dose 2.

The scenario depicted in [Figure 1](#) may be complicated if a subject receives a second vaccine dose before the control interval for the first dose has fully elapsed. In this situation, the first control period will be censored at the time of the second dose. Death of a subject during the control interval will also serve as a censoring event.

If a subject receives a second dose before the risk interval for dose 1 has completed, the risk periods will be concatenated and extended for the duration of the risk interval following the second dose. In this scenario, the SCRI analysis will include the -person time in the concatenated risk intervals and the control period following dose 2.

Details about AESI-specific risk intervals and washout periods will be specified in the SAP.

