For AESIs evaluated using SCRI, it is assumed that the occurrence of the event must not censor or affect the observation period, however, if such events are frequently fatal, this may relevantly impact the evaluation. To assess whether this outcome occurs, we will evaluate and report the number of fatal AESI that led to a censoring of the risk interval.

This study plans to estimate the risk of AESIs among subjects who have been vaccinated compared with unvaccinated with similar health conditions. Subjects who do not receive vaccination (or receive it later) may have different health status and patterns of healthcare compared with those who are vaccinated. These differences may include a higher prevalence of frailty or underlying chronic conditions ([Webster-Clark et al 2021](#)) among vaccinees. In studies involving vaccines, special attention should be given to bias related to **healthy vaccinee bias** and **confounding by indication** ([Remschmidt et al 2015](#)). While healthy vaccinee bias refers to the situation in which subjects who have better health conditions are more likely to be vaccinated; thus, confounding by indication may be present if subjects with underlying chronic diseases are more likely to be vaccinated than healthy study subjects. Although both situations could occur in this study, it is more likely that vaccination, at least at the beginning of the study period, will be preferentially directed to subjects with more underlying conditions. To address these potential bias/confounding issues, the current study is designed to first match subjects in the vaccinated cohort with comparators of the same age, sex, and at the same calendar date, and then use PS to adjust for potential confounders, including patterns of prior healthcare use.

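### SCRI control time ends at death and at the observed dose 2 date, so for AESIs that change either one the observation period depends on the event

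*Protocol*

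**What the plan says.** Section 9.1.2 reserves the SCRI for AESIs that meet several conditions. Two matter here: the event must not alter the chance of vaccination, and "the occurrence of the event of interest must not censor or affect the observation period".

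Section 9.2.3.2 gives the control interval the same length as the risk interval, apart from special circumstances that it then lists. Its worked example has a risk window of days 1-42. "After a 7-day washout period, the control interval begins and ends after 42 days as well", so control days are 50-91. The section says that the outcome itself does not censor and that "the full duration of the risk interval and control intervals factors into the analysis". Two exceptions follow. If dose 2 arrives before the dose 1 control interval is over, "the first control period will be censored at the time of the second dose". For death: "Death of a subject during the control interval will also serve as a censoring event". Only AESI-specific risk intervals and washout periods are left to the SAP, so these censoring rules are fixed in the protocol.

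Table 3 marks as SCRI-suitable, among others, myocardial infarction and ARDS (days 1-28), and Guillain-Barré syndrome, encephalitis, myocarditis/pericarditis and thrombosis without thrombocytopenia (days 1-42). Section 9.7.8 uses conditional Poisson regression. The primary analysis pools events after either dose, and analysis by dose is exploratory.

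Section 9.9.1 concedes that frequently fatal AESIs could matter and responds: "we will evaluate and report the number of fatal AESI that led to a censoring of the risk interval". Section 9.3.2 recognises that AESIs differ in how they affect later vaccination. No section says how the SCRI treats an AESI after dose 1 that changes dose 2.

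**The concern.** A self-controlled analysis is unbiased when the end of observation is unrelated to the event. Here both end points can be consequences of it.

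- **Death.** A case who dies of the event loses planned control time because of the event. If observation stops at any death, a fatal case in the risk window may have no control time at all and then contributes nothing to the conditional likelihood, while a fatal case in the control window still counts. The IRR is pulled down and a real risk can be masked.
- **Dose 2.** A person with an AESI after dose 1 may skip or postpone dose 2 and is then credited with the full control interval. Control events that count towards dose 1 could only arise before the scheduled dose 2. The IRR is pushed up and a false signal can appear.

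The SCRI contributes to primary objective 4. It is also the analysis that Section 9.9.1 turns to if comparable unvaccinated subjects become hard to find.

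**Working it through.** **The plan's own figure.** Section 9.5 gives about 70 events for 80% power at IRR 2, with half of observation time exposed and alpha 5%. In the signed-root-likelihood formula for self-controlled case series, with ρ = 2 and r = 0.5, ρr + 1 − r = 1.5, so:

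- A = 2[(1/1.5) ln 2 − ln 1.5] = 0.1133
- B = (ln 2)²/A × 0.5/1.5² = 0.943
- n = (1.960 + 0.842√B)²/A = 68.1, hence 69 events

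The figure reproduces. It assumes equal, complete intervals.

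**Inputs for the check.** From the protocol: risk length L = 42 or 28 days, 7-day washout and control length L (Section 9.2.3.2); dose 2 due 28-84 days after dose 1 (Section 7); conditional Poisson regression (Section 9.7.8). Assumed, because the documents give no values: fatality 10-30%, lag from event to death 0-30 days, and share q of dose 1 cases whose dose 2 is cancelled. The true IRR is 1, with one rare event uniform over risk and control days.

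**Estimating equation.** With y = 1 for an event in the risk interval, and R and C the credited risk and control days, the expected estimate θ solves Σ[y − Rθ/(Rθ + C)] = 0.

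**Death.** Let f be fatality, with death on the event day. A fatal control-window case on control day k is credited with C = k.

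- Only deaths inside the control interval censor: (1−f)[L − 2Lθ/(1+θ)] + f[L − Lθ/(1+θ) − Σₖ Lθ/(Lθ+k)] = 0. At L = 42, f = 0.1 and θ = 0.963, the terms are 0.9 × 0.79 = 0.71 and 0.1 × (21.40 − 28.55) = −0.72, which cancel to rounding.
- Any death ends observation: (1−f)[L − 2Lθ/(1+θ)] − f Σₖ Lθ/(Lθ+k) = 0. At θ = 0.864, 0.9 × 3.06 = 2.76 and 0.1 × 27.6 = 2.76.

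| Reading | 10% | 20% | 30% |
|---|---|---|---|
| Only deaths in the control interval, on event day (28 or 42 days) | 0.96 | 0.93 | 0.89 |
| Any death, on event day (28 or 42 days) | 0.86 | 0.73 | 0.60 |
| Any death, 30 days later, 42-day windows | 0.92 | 0.84 | 0.77 |
| Any death, 30 days later, 28-day windows | 0.95 | 0.89 | 0.84 |

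On the first reading, a 7-day lag with 42-day windows gives 0.98, 0.95 and 0.93.

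**Dose 2.** With 42-day windows and dose 2 due on day 77, control days 50-76 remain: 77 − 50 = 27. Dose 1 events then arise over 42 + 27 = 69 days. A case whose dose 2 is cancelled is credited with 42 control days; any other case with 27.

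- Dose 1 stratum: 42 = 69[qθ/(1+θ) + (1−q)42θ/(42θ+27)]
- Pooled, with the same daily event rate after each dose: 84 = 69[qθ/(1+θ) + (1−q)42θ/(42θ+27)] + 84θ/(1+θ)

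| q | 0% | 10% | 25% | 50% | 100% |
|---|---|---|---|---|---|
| Pooled (primary) | 1.00 | 1.02 | 1.05 | 1.10 | 84/69 = 1.22 |
| Dose 1 only (exploratory) | 1.00 | 1.05 | 1.12 | 1.25 | 42/27 = 1.56 |

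The dose 1 stratum at 25-50% cancellation gives 1.06-1.11 if dose 2 is due on day 84 and 1.43-1.97 if it is due on day 63. The q = 0 column shows that truncation at dose 2 is harmless in itself.

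**Scope.** With 28-day windows, control days are 36-63, so dose 2 on day 64 or later changes nothing. With 42-day windows, control time runs to day 91 and any dose 2 given by day 84 cuts into it.

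**Checks.** A simulation of 2,000,000 subjects gave 0.640 against 0.639 (any death, 30% fatality, 7-day lag) and 1.253 against 1.254 (dose 1 stratum, day 77, q = 50%). With interval ends that do not depend on the event, the null IRR is 1.000 even at 30% fatality and 50% cancellation.

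**The case against.** A reader might infer that Section 9.2.3.2 contradicts itself by promising full intervals and then cutting them. It does not: the section announces special circumstances, and dose 2 and death are those exceptions. The sentence on full duration explains that the outcome does not censor.

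A reader might also take 0.60 and 1.56 as the expected error. Neither is. The first needs any death to end observation, on the day of the event. The quoted sentence covers only deaths during the control interval, although Section 9.9.1 speaks of a censored risk interval, so the wording is ambiguous and both readings belong in view. The second needs every case to cancel dose 2 and sits in the exploratory dose 1 stratum.

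Further points on the plan's side are fair. Section 9.1.2 restricts the SCRI to AESIs that meet these assumptions, and Table 3 excludes TTS, thrombocytopenia with bleeding and sudden death. Section 9.9.1 discloses the fatality issue. The cohort is the primary approach. The interim reports found enough unvaccinated comparators; what fell short was follow-up for long risk windows, where the SCRI has little role.

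What remains is that Table 3 still admits AESIs that can be fatal or can plausibly affect dose 2, that the response on death is a count with no analysis, covering only the risk interval, and that event-dependent dose 2 is not addressed.

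**Conclusion.** The concern holds, conditionally. For AESIs that can cause death or move dose 2, the rules make the observation period depend on the event. For AESIs that do neither, the bias is zero.

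Under a true IRR of 1 and 10-30% fatality, the death rule gives about 0.96 to 0.89 on the narrow reading. On the broad reading it gives 0.86 to 0.60 with death on the event day, or 0.92-0.95 to 0.77-0.84 with a 30-day lag. The dose 2 rule (day 77, 42-day windows, 25-50% cancellation) gives 1.05-1.10 in the primary pooled analysis, assuming equal contributions by dose, and 1.12-1.25 in the dose 1 stratum. It mainly concerns windows of 42 days or longer.

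The two errors can partly offset: the narrow death rule at 10% fatality combined with 25-50% cancellation gives roughly 1.02 to 1.08 pooled. The net sign is therefore specific to the AESI. It would be tempting to conclude that the SCRI results are biased across the board. The documents do not support that, because they contain no fatality or deferral rates. This should be fixed, but it does not undermine the study, since the SCRI complements the primary cohort analysis.

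**What to change.** **(a) Death.** In Section 9.2.3.2, use the planned risk and control lengths in the main SCRI analysis whether or not the subject dies, truncating only for reasons unrelated to the event, such as end of data. Keep the death-censored version as a sensitivity analysis. Extend the Section 9.9.1 count to fatal events that censor the control interval.

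**(b) Dose 2.** Keep truncation at the observed dose 2 date in the main analysis. For AESIs whose control interval can reach dose 2, add two sensitivity analyses: one of dose 2 events only, and a dose 1 analysis whose control-time offset comes from the dose 2 timing of comparable AZD1222 vaccinees. Report dose 2 uptake and timing in cases against other vaccinees. The second analysis should include fatal cases: under (a), someone who dies before dose 2 counts as a cancelled dose 2, which at 10% fatality and day 77 leaves up to 1.02 pooled (1.05 for dose 1).

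**Cost.** Modest programming on data already held and lower precision in the dose-2-only analysis. The offset analysis assumes that cases would have followed the schedule of comparable vaccinees. This may fail if cases are frailer, which is why it belongs in a sensitivity analysis.

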## 9.3 Variables

### 9.3.1 Exposures

Receipt of AZD1222, other COVID-19 vaccines, and dates of vaccination will be obtained from all possible sources that capture COVID-19 vaccination, such as pharmacy dispensing records, general practice records, and immunisation registers. Depending on the data source, vaccines will be identified via nationally used product codes, where possible. The extent of capture of COVID-19 vaccination in the target populations and of specific product types is not

currently known in candidate data sources. The duration of the risk periods will be specific for each of the outcomes and defined to establish an accurate relationship and patterns in that relationship (Section 9.3.2). Algorithms and codes to ascertain relevant vaccinations will be included in the SAP.

### 9.3.2 Outcomes

Outcomes include the safety concerns and other AESIs listed in the current approved AZD1222 EU RMP and also new safety events of interest raised by the EMA after evaluation of cases involving thrombocytopaenia with thrombosis or bleeding. The AESIs differ in terms of latency, acuity of onset, availability of empirical estimates for appropriate risk periods, and the effect of the event on subsequent likelihood of vaccination. Table 3 lists these AESIs, indicates which of the events are deemed suitable for analysis using SCRI analysis, and indicates the proposed risk interval for those that are deemed suitable. In addition, risk intervals are proposed for some AESIs that are deemed not suitable for SCRI. Although available evidence suggests that any biological effect of a vaccine is expected to occur during these intervals, uncertainty about the end of this period raises concerns about misclassification bias that could occur if the control interval (which follows the risk interval in the proposed SCRI analysis) includes person-time that is actually at risk. The Sponsor also judges that it is reasonable to use these intervals in the cohort analysis. This allows for more certainty that comparator person-time does not include time at risk (barring unrecorded vaccinations). Person-time remote from the vaccination date is deemed very unlikely to be at risk from any adverse vaccine effect, and to include it could substantially attenuate estimates of a vaccine-associated risk that operated only closer to the index date. There is, of course, the potential cost of this approach limiting the number of outcomes, but we judge that the trade-off is reasonable to reduce misclassification bias that could mask a true signal.

**Table 3 Adverse Events of Special Interest and Other Safety Concerns**

Adverse event	Suitable for SCRI analysis according to ACCESS protocol template a	Risk interval after index date (days)	Clean look-back interval (days) k
Vaccine-associated enhanced disease, including vaccine-associated enhanced respiratory disease, including ARDS	No	14-365 b	365
Multisystem inflammatory syndrome in adults/children	Yes	1-42 c	365 c
Sudden death	No	0-6 b	Not applicable
Autoimmune thyroiditis	No d	1-180 e	365
Anosmia, ageusia	No f	1-365 e	365
Anaphylaxis	Yes	0-2 c	180 c

**Table 3 Adverse Events of Special Interest and Other Safety Concerns**

Adverse event	Suitable for SCRI analysis according to ACCESS protocol template a	Risk interval after index date (days)	Clean look-back interval (days) k
Type III hypersensitivity reactions	No d	1-365 e	365
ARDS	Yes	1-28 j	365
Guillain-Barré syndrome	Yes	1-42 c	365 c
Other peripheral and polyneuropathies	No d	1-42 c	365 c
Multiple sclerosis, and other demyelinating disorders	No d	1-365 e	365 c
Transverse myelitis	Yes	1-90 c	365 c
Optic neuritis/neuromyelitis optica spectrum disorder	Yes	1-42 c	365 c
Encephalitis (including acute disseminated encephalomyelitis)	Yes	1-42 b	183 c
Myasthenia gravis	No d	1-365 e	365
Bell's palsy	Yes	1-42 c	365 c
Generalised convulsions	Yes	0-14 c	365
Narcolepsy	No	1-42 c	365 c
Myocarditis/pericarditis	Yes	1-42 c	365 c
Postural orthostatic tachycardia syndrome	No d	1-42 b	365 c
Myocardial infarction	Yes	1-28 c	365 c
Acute cardiac injury including microangiopathy, cardiogenic shock, and heart failure	No f	1-90 e	365
Stress cardiomyopathy	No f	1-42	365
Thrombocytopenia	Yes	1-42 b	365 c
Thrombocytopenia with associated bleeding	No d	1-42 g	365 c
Thrombosis (embolic and thrombotic events) without thrombocytopenia	Yes	1-42 c	365 c
Thrombosis with thrombocytopenia syndrome	No d	1-42 g	365
Capillary leak syndrome	No d	1-365 e	365
Acute kidney injury	Yes	1-14 b	365
Acute liver injury	Yes	1-14 b	365
Acute pancreatitis	No d	1-365 e	365

**Table 3 Adverse Events of Special Interest and Other Safety Concerns**

Adverse event	Suitable for SCRI analysis according to ACCESS protocol template a	Risk interval after index date (days)	Clean look-back interval (days) k
Acute aseptic arthritis	Yes	1-42 b	365
Fibromyalgia	No d	91-365 h	365
Rhabdomyolysis	No d	1-42 b	365
Chronic fatigue syndrome/ME/PVFS	No d	183-365 i	365
Erythema multiforme	No f	1-365 e	365
Chilblain-like skin lesions	No f	1-365 e	365

a Suitability according to ACCESS protocol template entitled “Safety evaluation of COVID-19 vaccines in electronic healthcare databases.” See Section 9.1.2 and Section 9.2.1.3 for additional information on SCRI design.

b Risk interval based on consensus definition from the AESI Working Group of Vaccines Europe, March 2021.

c Based on Lee et al (2011) or COVID-19 Vaccine Safety Surveillance: Active Monitoring Master Protocol (FDA 2020).

d Not addressed in ACCESS protocol template but is deemed not suitable for one or more of the following reasons: onset may be gradual, the diagnosis date may substantially lag the onset of symptoms, or the risk period is not clearly established.

e No consensus evidence for a risk period was identified; defaults to 1 year following index date.

f ACCESS protocol template indicates “yes,” or SCRI may be suitable if a purported risk period can be identified, which is not yet known for this AESI. Absent such information, deemed not suitable.

g Sensitivity analyses will evaluate alternative risk windows. For TTS, they will be 1-14, 1-21, and 1-28 days after the index date. For thrombocytopenia with bleeding, the alternative risk window will be 1-28 days after the index date, following Pottegård et al (2021).

h No consensus evidence for a risk period was identified. However, because symptoms need to be present for at least 3 months before subjects qualify for the diagnosis (Arnold et al 2019), the start of the risk window was set to 91 days after the index date.

i No consensus evidence for a risk period was identified. However, because chronic fatigue needs to be present for at least 6 months before subjects qualify for the diagnosis (IOM 2015), the start of the risk window was set to 183 days after the index date.

j Based on Serazin et al (2021).

k Clean interval refers to the look-back period before cohort entry during which no AESI was observed. Unless indicated otherwise, the interval duration is based on the clinical judgement of the research team.

Note: Risk window definitions may evolve during the course of the study as more knowledge is gathered about individual AESIs.

AESI, adverse event of special interest; ARDS, acute respiratory distress syndrome; COVID-19, coronavirus disease 2019; FDA, Food and Drug Administration; IOM, Institute of Medicine; ME, myalgic encephalitis; PVFS, postviral fatigue syndrome; SCRI, self-controlled risk interval; TTS, thrombosis with thrombocytopenia syndrome.

Outcomes will be identified using algorithms based on codes for diagnoses, procedures, and treatments in electronic data, and they will be defined uniformly across the data sources to the fullest extent possible. Operational case definitions from the ACCESS project ([https://drive.google.com/drive/folders/1Y\\_3cuGRN1g-jBv2ec1fC0aYcpxEjtrY9](https://drive.google.com/drive/folders/1Y_3cuGRN1g-jBv2ec1fC0aYcpxEjtrY9)) will be

implemented for the AESIs for which they have been developed. The SAP will include detailed information on codes and algorithms.

If feasible, algorithms to identify selected AESIs will be validated in a sample of cases based on manual review of electronic records or chart abstraction conducted by clinicians blinded to COVID-19 vaccine exposure. If validation is performed, certainty of an event diagnosis will be classified against existing and as-yet developed standardised definitions such as those created by the Brighton Collaboration.

### 9.3.2.1 Thrombosis With Thrombocytopenia Syndrome

As previously noted, case definitions will be specified in the SAP, however, given its clinical importance, additional details for defining TTS are provided here. As of May 2021, no TTS standard case definition has been accepted for use by all countries ([Brighton Collaboration 2021b](#)). The Brighton Collaboration interim case definition for TTS (version 10.16.2, 18 May 2021) defines TTS as “Any patient presenting with both acute venous or arterial thrombosis AND new-onset thrombocytopenia (TCP)” [as confirmed by both the Brighton Case Definitions for thrombocytopenia and thrombosis ([Brighton Collaboration 2021a](#), [Wise et al 2007](#))]. The Brighton Collaboration case definition for TCP ([Wise et al 2007](#)) requires evidence of a platelet count of less than  $150,000/\mu\text{L}^3$ .

[figure not shown]
Because laboratory measurements of platelet counts are not expected to be available for most proposed data sources, the case definition of TTS for the current study has been adapted to qualify TCP based on a diagnosis code. In addition, diagnoses that qualify for thrombosis do not include acute myocardial infarction (AMI) or stroke, which is consistent with the May 2021 Centers for Disease Control and Prevention (CDC) working case definition for TTS following COVID-19 vaccination ([CDC 2021](#)). It should be emphasised that the proposed case definition for this study is provisional and subject to change as the Brighton case definition evolves and in response to findings from validation exercises. Because the concept of “thrombosis” also includes embolic events, for purposes of the case definition, the concept has been relabeled “thromboembolic event” (TE).

The working TTS case definition for this study requires:

- A new qualifying TE (defined below) AND
- A new diagnosis of TCP (or laboratory evidence of the same, where available) that is made from 10 days before and up to 10 days after that event (<https://zenodo.org/record/5255870#.Yx8KBHZBxPZ>) ([Burn et al 2022](#))

[Figure 5](#) shows the look-back (“washout”) periods proposed to define “new” diagnoses.

